10.0 STUDY VISITS AND PROCEDURES

10.1 Study Calendar

The procedures performed at each study visit are listed in the table below.

Procedure/Visit	Screening	Baseline	Obtain MSCs ²	MSC IMP Injection	Follow-up visit						
					3-day phone call ⁹	1-week phone call ⁹	1-month	3-month	6-month	12-month	24-month
Visit window											
Day ± days	- 42 ± 14	- 42 ± 14	- 28 ± 14	0	3 ± 2	7 ± 2	30 ± 10	90 ± 14	180 ± 21	365 ± 21	730 ± 28
Informed Consent	X										
Review Eligibility Criteria	X										
Demographics	X										
Review Concomitant Medications	X				X	X	X	X	X	X	X
Dental Evaluation ⁵		X									
Obtain Medical History		X									
Physical Exam		X					X	X	X	X	X
Vital Signs ¹		X		X ³			X				
Bone Marrow Aspiration			X								
MSC IMP Injection				X							
AE Assessment Including Pain			X	X ⁴	X	X	X	X	X	X	X
Assessment of QoL, Salivary Collection		X					X	X	X	X	X
Ultrasound of Salivary Glands		X						X	X	X	
Collection of Pain Diary ⁶							X				
Blood (for banking)		X					X	X	X	X	X
Complete blood count, PT/INR and PTT, Creatinine		X					X ⁸	X ⁸			
Pregnancy test (urine or serum)			X ⁷	X ⁷							

¹ – Vitals include body weight, pulse rate, body temperature, blood pressure, and respiration rate. Height collected only at baseline.

² – Subjects will be contacted via phone 3 days +/- 2 days post bone marrow aspiration to assess for toxicities from aspiration by study coordinator

³ – Vitals to be obtained pre injection and 30 minutes +/- 10 minutes post injection. Weight only obtained pre injection.

⁴ – Subjects will be asked to verbally rate their pain 30 minutes post MSC administration.

⁵ – Dental examination with x-rays within 6 months of enrollment by patient report

⁶ – Patients without chronic pain will be instructed to refrain from narcotic pain medication for 3 days prior to their scheduled pain assessment. Patients with chronic pain will be instructed not to increase their baseline narcotic pain medication for 3 days prior to scheduled pain assessment.

⁷—Within 7 days prior to MSC collection and confirmation of appropriate contraception prior to injection.

⁸—CBC only during follow up

⁹-Subjects will be contacted via phone 3 days (+/- 2 days) and 7 days +/- 2 days post MSC IMP Injection to assess for toxicities from injection by study coordinator or physician.

Sub study calendar

Informed Consent	Screen/Injection of MSC's	Phone call (3 days +/- 2 days) ¹	Phone call (7 days +/- 2 days) ¹	30 day visit (+/-10 days)	90 days (+/- 14 days)	6 months (+/- 28 days)	12 months (+/- 3 months)	24 months (+/- 3 months)
Review Eligibility Criteria	X							
Review Concomitant Medications	X							
Vital Signs ²	X							
Physical	X			X	X	X	X	X
MSC IMP Injection (contralateral neck)	X							
AE Assessment Including Pain	X ³	X	X	X	X	X	X	X
Assessment of QoL, Salivary Collection	X			X	X	X	X	
Collection of Pain Diary				X				
Complete blood count	X			X ⁴	X ⁴			

¹Subjects will be contacted via phone 3 and 7 days +/- 2 days post MSC IMP Injection to assess for toxicities from injection by study coordinator or physician

²Vitals to be obtained pre injection and 30 minutes +/- 10 minutes post injection. Weight only obtained pre injection.

³— Subjects will be asked to verbally rate their pain 30 minutes post MSC administration. Patients without chronic pain will be instructed to refrain from narcotic pain medication for 3 days prior to their scheduled pain assessment. Patients with chronic pain will be instructed not to increase their baseline narcotic pain medication for 3 days prior to scheduled pain assessment

⁴CBC only during follow up

10.2 Screening and Enrollment

The Screening and study visits and procedures are described in detail below.

Informed Consent

The informed consent process will be conducted following all federal and institutional regulations relating to informed consent. Informed consent will be obtained prior to conducting any research-related activities.

The informed consent process will be performed as follows:

- The research coordinator will review the informed consent form and discuss the study in detail with the potential research subject.
- The research coordinator will explain the study, its risks and benefits, what would be required of the research subject, and alternatives to participation.
- The research subject will be given the opportunity to take the informed consent form home so that they may discuss it with family members, friends, clergy or others when possible.
- The subject will have the opportunity to ask questions and have all questions answered by the research coordinator and/or PI.
- The informed consent document must be signed and dated by the research subject and by the study team member performing consent procedures.
- The research coordinator will review the informed consent document to ensure that all fields that require a response are complete (i.e., checkbox marked yes or no, etc.) as applicable.
- The research subject will be given a copy of the signed and dated informed consent form.

Alternatively remote consenting may occur as described below:

- The participant must receive a copy of the ICF (e.g., in person, via mail, fax, email, or a Part 11 compliant manner will be used to document consent) in advance of discussion.
- The study coordinator discusses the study with the potential participant via telephone or video conferencing.
- The study coordinator must implement a method to ensure the identity of the participant (e.g., verification of state identification or other identifying documents or use of personal questions such as date of birth or spell first and last name).
- If the potential participant agrees to participation, they must sign and date the ICF and return it to the study coordinator via email using a scanner or taking a picture of the signature page or using a Part 11 compliant manner to document consent.
- The study coordinator will document the receipt of the signed ICF and the informed consent process in the Electronic Medical Record (Healthlink).
- The study coordinator must then email [contact] a PDF of the participant's signed ICF to be uploaded in Healthlink. As soon as the consent note is written in Healthlink and consent form has been emailed for scanning, screening procedures may begin.
- No additional signatures are required.

Enrollment/Registration

A research subject will be defined as "enrolled" in the study when they meet the following criteria:

- The subject has been consented by study staff.
- The subject has completed all screening procedures.
- The PI has verified subject eligibility by reviewing inclusion and exclusion criteria
- The subject has been enrolled by the protocol staff in the UWCCC ONCORE database.

The following information will be recorded:

- Protocol number
- Patient's name and initials
- Patient's medical record number
- Patient demographic data

Screening

- Information from SOC clinic visits may be used if within study window. No research only procedures will occur prior to obtaining written informed consent.
- All screening procedures must be performed prior to study enrollment/registration.
- Record data on disease characteristics (e.g., site, stage) and treatment characteristics (e.g., radiation dose distributions)

- Review current medications being taken (SOC)
- Obtain written informed consent

10.3 On-Study/Follow-up Visits

After subjects have been enrolled, the On-Study/Follow-up visit and the procedures performed at each visit are described in detail below.

Baseline (may occur over 1-2 visits)

- Physical exam including weight and height and med history (SOC)
- Vital signs (SOC)
- Ensure patient has undergone dental evaluation with radiographs to exclude dental/oral diseases that could cause treatable xerostomia within 6 months of enrollment
- Salivary collection (research)
- QoL assessment (research)
- Collection of blood sample for banking purposes (research)
- US of salivary glands (research)
- Review of RT DICOM file of head and neck radiation plan (research)
- Complete blood count PT/INR, PTT and creatinine (research)

Bone Marrow Aspiration for MSC Collection

- Bone marrow aspiration

MSC IMP Administration

- Review current medications being taken
- Vital signs
- MSC injection (see section 9.6)
- Patients without chronic pain will be instructed to refrain from narcotic pain medication for 3 days prior to their scheduled pain assessment. Patients with chronic pain will be instructed not to increase their baseline narcotic pain medication for 3 days prior to scheduled pain assessment.

Assessments **after** MSC IMP administration

- Acute toxicity: vital signs (pre and 30 minutes +/- 10 minutes post) and visual inspection of injection site **after** the administration of IMP: 30 minutes post-injection and monitoring of adverse events possibly related to acute toxicity including verbal pain assessment.

Three Day Telephone Call (3 days \pm 2 days)

- Adverse event assessment

One Week Telephone Call (7 days \pm 2 days)

- Adverse event assessment
- Obtain description of injection area

One Month Follow-up Visit (30 days \pm 10 days)

- Review current medications being taken
- Physical exam including weight
- Vital signs
- Salivary collection
- QoL assessment
- Adverse event assessment
- Collection of blood sample for banking purposes

- Collection of pain diary
- Complete blood count,

Three Month Follow-up Visit (90 days \pm 14 days)

- Review current medications being taken
- Physical exam including weight
- Salivary collection
- US of salivary glands
- QoL assessment
- Adverse event assessment
- Collection of blood sample for banking purposes
- Complete blood count

Six Month Follow-up Visit (180 days \pm 21 days)

- Review current medications being taken
- Physical exam including weight
- Salivary collection
- US of salivary glands
- QoL assessment
- Adverse event assessment
- Collection of blood sample for banking purposes

Twelve Month Follow-up Visit (365 days \pm 21 days)

- Review current medications being taken
- Physical exam including weight
- Salivary collection
- US of salivary glands
- QoL assessment
- Adverse event assessment
- Collection of blood sample for banking purposes

Twenty Four Month Follow-up Visit (730 days \pm 56 days)

- Review current medications being taken
- Physical exam including weight
- Salivary collection
- QoL assessment
- Adverse event assessment
- Collection of blood sample for banking purposes

Screening/MSC IMP Administration in Contralateral Gland

- Physical exam including weight
- Salivary Collection
- QoL assessment
- MSC injection (see section 9.6)
- Vital signs

Three Day Telephone Call (3 days \pm 2 days)

- Adverse event assessment

Seven Day Telephone Call After Contralateral Injection (7 days \pm 2 days)

- Adverse event assessment

Thirty Day Follow-up Visit After Contralateral Injection (30 days \pm 10 days)

- Physical exam including weight
- Adverse event assessment
- Complete Blood Count
- Salivary Collection
- QoL assessment

Ninety Day Follow-up Visit After Contralateral Injection (90 days \pm 14 days)

- Physical exam including weight
- Adverse event assessment
- Complete Blood Count
- Salivary Collection
- QoL assessment

Six Month Follow-up Visit (180 days +/- 28 days)

- Physical exam including weight
- Salivary collection
- QoL assessment
- Adverse event assessment

Twelve Month Follow-up Visit After Contralateral Injection (12 months \pm 3 months)

- Physical exam including weight
- Adverse event assessment
- Salivary collection
- QoL assessment

Twenty Four Month Follow-up Visit (730 days +/- 3 months)

- Physical exam including weight
- Adverse event assessment

Note: This twenty four month visit will be the subject's final study visit.

10.4 Unscheduled Visits

Notes from unscheduled visits for pain or swelling will be reviewed by the PI to assess for study-related AE/SAE. Whenever appropriate unscheduled visits will be with a study team member.

10.5 Early Termination/Withdrawal Visit

If a patient prematurely discontinues the study for any reason after administration of the MSC IMP, all assessments planned for the final follow-up visit (24 months) should be performed. The reason for premature discontinuation will be documented.

11.0 COLLECTION AND PROCESSING OF PATIENT REPORTED OUTCOMES, BIOSPECIMENS, AND IMAGING

11.1 Pain Measurement

Subjects will be asked to rate their pain on a scale from 0 -10 (0=not at all to 10=worst pain imaginable) by referring to a provided visual analog pain scale. The pain scale of 0-10 has been validated to allow for the discrimination of clinically meaningful differences in pain^{31,32}. They will be asked to rate their pain at baseline (screening), 30 minutes after the MSC IMP administration, 3 days after administration, one week after administration, 30 days after, and 90 days after MSC administration. Subjects will additionally keep a diary with daily entries to record occurrence and severity of pain and occurrence and severity of other adverse events (redness, swelling, warmth, tenderness, rash, pruritis, nausea, vomiting, fatigue etc.) for the first month after MSC injection. Subjects will also keep a log of all pain medications used during the first 30 days, including narcotic and non-narcotic medications.

11.2 Quality of Life Assessments

Quality of life will be assessed using three validated tools: the University of Michigan Xerostomia Related Quality of Life (XeQOL) scale³³, the MD Anderson Dysphagia Index (MDADI)³⁴, and the VAS xerostomia questionnaire³⁵.

The University of Michigan Xerostomia related quality of life scale (XeQOL) is a validated patient-reported 15-item assessment scale with 4 domains: physical functioning, pain/discomfort, personal/psychologic functioning, and social functioning (Appendix 19.1). The score is the average of all responses of all domains and can range from 0 to 4. Higher scores indicate increased xerostomia burden. This scale has high reproducibility and sensitivity.

The MDADI is a 20-item questionnaire designed for evaluating the impact of dysphagia on the QOL of patients with head and neck cancer. The questionnaire and scoring instructions are in Appendix 19.2.

The VAS xerostomia questionnaire is an 8-item questionnaire that provides a validated measure of the perception of dry mouth. Subjects will be asked to mark their responses to each item by placing a vertical line on the 100-mm horizontal scale. The questionnaire is in Appendix 19.3.

Subjects will complete the XeQoL, MDADI, and VAS at the screening (baseline) visit and at 3- and 6-month follow-up visits. Subjects in the dose-escalation cohort will also complete these QoL questionnaires at their one-month follow-up visit.

11.3 Salivary Flow Rate Assessments

Whole saliva production rates (sialometry) will be measured under unstimulated and stimulated saliva collection conditions, as previously described^{36,37}. Participants will refrain from eating, drinking, and,

smoking for one hour prior to collection. Unstimulated saliva production will be measured first by the passive drool method over a 5-minute time frame. Participants will allow saliva to pool in the mouth and, then, with head tilted forward, gently guide saliva into a saliva collection aid attached to a cryovial. Stimulated saliva production will be measured by having participants chew inert gum base to the pace of a metronome (70 beats per minute) while expectorating saliva (without swallowing) into the saliva collection aid for 5 minutes total³⁸. Cryovials will be weighed before and after collection and the difference in weight (g) will represent the amount of saliva produced in 5 minutes for each condition. Subjects will complete the salivary flow rate assessments at the screening (baseline) visit and at 1-, 3-, 6-, 12-, and 24-month follow-up visits.

11.4 Salivary Composition Analyses

Salivary composition analyses will focus on qualitative aspects of saliva previously found to change following radiation treatment: salivary pH^{39,40}, total protein concentration (mg/mL)^{41,42}, amylase (mU/mL)^{39,43}, and mucins (MUC5B, mU/mL)^{43,44}. Given that MSCs will be injected into one of the submandibular glands which contain both serous and mucous acinar secretory cells, we will measure products of both types of cells (both= total protein and pH; serous= amylase; mucous= mucins). Salivary pH will be measured using a pH meter (Orion 9810BN, Thermo Scientific). Enzyme-linked immunosorbent assays (ELISAs) will be used to quantify total protein, amylase, and mucin levels. Saliva composition will be assessed on whole saliva samples collected from subjects at each timepoint salivary flow rate is assessed (see Section 11.3). Saliva will be processed, stored at -80C, and analyzed in batch at a later date.

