12.3 Retention for Future Research: Data & Biospecimen Banking

Purpose of Storage

The purpose of collecting and storing biospecimens is to establish a biobank for use by UW-Madison researchers to use who are investigating the causes, diagnosis, prevention and treatment of cancer.

Data and/or Biospecimens Being Stored

Blood in a 3 mL standard EDTA tube will be collected from each participant on the day of bone marrow biopsy, and at the 1(for those seen at 1 month), 3, 6, 12, and 24 month follow-ups. This blood will be labeled with a unique subject ID code. All tubes of blood will then be stored in a secure freezer in the secured [name] lab in WIMR.

Saliva will be collected from each participant at the pre-specified timepoints as detailed previously. The saliva will be used for clinical endpoints as detailed previously, any remaining saliva will be stored in an Eppendorf tube in a secure freezer in the secured [name] lab in WIMR.

Location of Storage

Blood and saliva tubes labelled with coded subject ID number, date, and time point, will be stored in the [name] Laboratory. Data associated with the blood and saliva tubes is on a UW password-protected server.

Duration of Storage

Biospecimens will be stored until they are used up in their entirety.

Access to Data, Images, Recordings and/or Biospecimens and Security Measures

UW researchers who are doing biomedical research may apply for access to coded data and blood (no patient identifiers on tube).

Procedures to Release Data or Biospecimens

Researchers must have local IRB approval for their study which will include study of the biospecimens and accompanying data.

Process for Returning Results

There are no plans to disclose results of future testing to research subjects.

Process for Tracking Subject Consent and Authorization

In the consent form for this study, subjects are informed of an optional aspect of the study that involves donating blood for future biomedical research. Subjects are made aware they do not have to donate biospecimens to the Biobank to participate in the study. Subjects must opt into the biobanking aspect of the study by checking a box and initialing a line next to the box.

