13.8 Analyses of the Secondary Endpoints

Analyses of the secondary endpoints focus on efficacy of the IMP in the treatment of xerostomia and hyposalivation. All inferential analyses for the secondary outcome variables will be interpreted in the exploratory sense, only.

Patient-reported outcome measures will be evaluated by comparing the changes in salivary QOL from baseline to each follow-up visit and by assessing changes over time, within-group comparisons will be performed with the Wilcoxon signed-rank test.

Salivary flow rate analysis will be analyzed in a manner described by Gronhoj et al. 2018²⁴: by comparing the changes from baseline to each follow-up visit and changes over time, within-group comparisons will be performed with the Wilcoxon signed-rank test.

Salivary composition analyses will focus on qualitative aspects of saliva previously found to change following radiation treatment: salivary pH^{39,40}, total protein concentration (mg/mL)^{41,42}, amylase (mU/mL)^{39,43}, and mucins (MUC5B, mU/mL)^{43,44}. Given that MSCs will be injected into one of the submandibular glands which contain both serous and mucous acinar secretory cells, we will measure products of both types of cells (both= total protein and pH; serous= amylase; mucous= mucins). Salivary pH will be measured using a pH meter (Orion 9810BN, Thermo Scientific). Enzyme-linked immunosorbent assays (ELISAs) will be used to quantify total protein, amylase, and mucin levels. Saliva composition will be assessed on whole saliva samples collected from subjects at the screening visit and the in-person follow-up visits.

To assess the imaging characteristics of submandibular gland after MSC injection, salivary gland size will be measured by ultrasound⁴⁵. Ultrasound imaging is a non-ionizing, noninvasive imaging modality that can be quickly obtained in a standard exam room. Three-dimensional (3D) Bmode data sets will be acquired for tumor volume measurements. If post-RT submandibular glands suppress ultrasound waves to prevent the visualization of the lower outline of the gland, a 2D estimate of gland size will be made.

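### Total protein is assigned to ELISA, which cannot measure it, and the plan does not say whether salivary pH is read before or after freezing

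*Combined protocol and SAP*

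**What the plan says.** Compositional analysis is part of the secondary efficacy endpoint (sections 3.1 and 6.0). Section 11.4 names four measures: pH, total protein, amylase and MUC5B. It treats pH and total protein as the two that reflect both serous and mucous cells.

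- **Total protein.** Section 11.4 lists it as "total protein concentration (mg/mL)". The assay sentence, which stands in both 11.4 and 13.8, is "Enzyme-linked immunosorbent assays (ELISAs) will be used to quantify total protein, amylase, and mucin levels".
- **pH.** Section 11.4 says "Salivary pH will be measured using a pH meter (Orion 9810BN, Thermo Scientific)" and gives no time of reading.
- **Samples.** Section 11.4: "Saliva composition will be assessed on whole saliva samples collected from subjects at each timepoint salivary flow rate is assessed", which by 11.3 means baseline and months 1, 3, 6, 12 and 24. Section 13.8: "Saliva composition will be assessed on whole saliva samples collected from subjects at the screening visit and the in-person follow-up visits".
- **Handling.** Section 11.4 ends with "Saliva will be processed, stored at -80C, and analyzed in batch at a later date". Section 13.8 repeats the pH and ELISA methods without mentioning freezing. Section 12.3 says that after endpoint use "any remaining saliva will be stored in an Eppendorf tube in a secure freezer".

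**The concern.** Two of the four composition measures have a measurement problem as written, and they are the two the plan relies on to reflect both cell types.

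For total protein, the named method does not produce the listed quantity. A laboratory that follows the text has no valid way to report it.

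For pH, the freezing sentence covers all composition measures on its face. Salivary pH depends on dissolved carbon dioxide and bicarbonate, so a reading taken after processing, freezing and thawing may differ from the value at collection. If samples from all visits are also held for one late batch, storage time is ordered by visit. With no control group, a storage effect and a treatment effect on pH would look the same.

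**Working it through.** The plan gives no figure to reproduce here. The check compares sections and adds one subtraction.

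**1. Does the named assay give the listed quantity?** The quantity is total protein in mg/mL (11.4). The method is ELISA (11.4, repeated in 13.8). An ELISA uses antibodies against a specific target and returns the amount of that target. Total protein is the sum over all proteins in the sample. The two do not match, and no other total-protein method appears anywhere in the document. Because the sentence is repeated, it is not a slip in one place. This step rests on the principle of the assay, not on a figure in the plan.

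**2. When is pH read?**

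| Place | What it settles |
|---|---|
| 11.3, collection procedure | Saliva goes into a cryovial, which is weighed before and after. No pH step. |
| 10.1 and 10.3, calendars and visit lists | Saliva collection only. No pH reading at any visit. |
| 11.4 | pH meter named. Freezing and batching come later in the same paragraph, with no exception for pH. *Processed* is not defined. |
| 13.8 | pH meter named, freezing not mentioned. |
| 12.3 | Leftover saliva is stored after endpoint use. Does not say when pH is read. |

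Read literally, pH falls under the freeze-and-batch sentence. A fresh reading is placed nowhere and ruled out nowhere. The timing is therefore unspecified.

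**3. How far would storage times differ?** Assumption: one batch, run after the last visit. The plan does not state how batches are made up.

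Inputs: baseline at day −42 ± 14 (10.1); month 24 at day 730 ± 28 (10.1) or day 730 ± 56 (10.3). The two sections disagree on the month-24 window, so both are used.

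Difference in storage = day of month-24 sample − day of baseline sample.

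- Nominal: 730 − (−42) = 772 days.
- With ±28: shortest (730 − 28) − (−42 + 14) = 702 + 28 = 730 days; longest (730 + 28) − (−42 − 14) = 758 + 56 = 814 days.
- With ±56: shortest (730 − 56) − (−28) = 674 + 28 = 702 days; longest (730 + 56) − (−56) = 786 + 56 = 842 days.

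At nominal days, the other visits are stored longer than month 24 by 730 − 30 = 700 days (month 1), 730 − 90 = 640 (month 3), 730 − 180 = 550 (month 6) and 730 − 365 = 365 (month 12).

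**4. What would that do to a change from baseline?** Write each reading as true pH + h + g(t). Here h is a handling shift common to all visits and g(t) is any drift after t days at −80C. If month-24 saliva has been stored T days, then

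observed change = true change − [g(T + 772) − g(T)].

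The common shift h drops out. What remains is drift that depends on storage time. The documents give no value for g, so no size in pH units can be attached to it. Section 13.2 compares timepoints by one-way ANOVA with Tukey's method in a single group (7.1). Nothing in that analysis would separate g from a real change.

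**The case against.** The strongest reply concerns pH. The pH-meter sentence precedes the storage sentence, *processed* could include a fresh reading, and 12.3 and 13.8 leave one possible. That stands. A reader might infer that the plan has pH measured on altered samples. The documents support only that the time of reading is not stated.

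A reader might also infer that pH is biased in a direction tied to visit, with the same sign in every subject. That does not follow. Carbon dioxide loss and a freeze-thaw cycle would affect every visit if handling is the same, and such a shift largely cancels in the change from baseline. Only drift that accumulates with storage time would follow visit order. The documents neither show such drift nor say that all visits go in one late batch.

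The amylase unit is a tempting further target, since mU/mL is ordinarily an activity unit and ELISA measures antigen. But 11.4 uses the same unit for MUC5B, so it may simply be a kit unit. That supports a check of units, not a finding of error.

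Finally, these measures are exploratory (13.1, 13.8), in six to twelve subjects. That limits the consequence. It does not excuse naming an assay that cannot give the listed quantity.

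**Conclusion.** The total-protein point holds without assumptions about conduct: 11.4 and 13.8 name a method that cannot yield total protein concentration, and no alternative is given.

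The pH point holds as a gap with a possible consequence. The plan does not say whether pH is read before or after freezing, its literal text points to after, and a thawed reading may not reflect salivary pH. Two conditions must both be met before change over time is affected: pH is read on stored saliva, and storage time differs by visit. Under a single batch after the last visit, the baseline-to-month-24 difference is about 772 days (730 to 814 with the ±28-day window, 702 to 842 with ±56). The resulting error in pH units is unknown.

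The point is worth correcting because the fix is cheap and these are the two measures assigned to both cell types. It does not touch the primary endpoint, which is based on dose-limiting toxicity.

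**What to change.** In sections 11.4 and 13.8:

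1. Replace ELISA with a named total-protein assay for total protein. Keep ELISA for the specific targets.
2. State that pH is read with the meter already named, on a fresh aliquot, at a fixed time after collection and before freezing. If this has been the practice, one sentence saying so closes the pH point.
3. If any earlier visits were read only after thawing, compare pH only between visits handled the same way. For subjects who have the contralateral injection, the sample taken just before it can start a fresh series.
4. Confirm that the amylase and MUC5B units are those the chosen kits report.

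The cost is assay wording and a few minutes per visit. The downside is that some earlier pH readings may not be comparable with fresh ones. The formal SAP is still to be written before database lock (section 13.0) and can carry the same wording.
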